8.4.4 TIME PERIOD AND FREQUENCY FOR EVENT ASSESSMENT AND FOLLOW-UP

The occurrence of an adverse event (AE) or serious adverse event (SAE) may come to the attention of study personnel during study visits and interviews of a study participant presenting for medical care, or upon review by a study monitor.

All AEs, including local and systemic reactions not meeting the criteria for SAEs, will be captured in the source and on the appropriate case report form (CRF) within 7 days of awareness. Information to be collected includes event description, date and time of onset, clinician's assessment of severity, relationship to study product (assessed only by those with the training and authority to make a diagnosis), and date and time of resolution/stabilization of the event. All AEs occurring while on study must be documented appropriately regardless of relationship. All AEs will be followed to adequate resolution.

Any medical condition that is present at the time that the participant is screened will be considered as baseline and not reported as an AE. However, if the study participant's condition deteriorates at any time during the study, it will be recorded as an AE.

Findings of the EGD procedure are part of the primary endpoint of the study, and should not be recorded as Adverse Events.

Changes in the severity of an AE will be documented to allow an assessment of the duration of the event at each level of severity to be performed. AEs characterized as intermittent require documentation of onset and duration of each episode.

Site study staff will record all reportable events with start dates occurring any time after informed consent is obtained until 7 (for non-serious AEs) or 30 days (for SAEs) after the last day of study participation. At each study visit, the investigator will inquire about the occurrence of AE/SAEs since the last visit. Events will be followed for outcome information until resolution or stabilization.

8.4.6 SERIOUS ADVERSE EVENT REPORTING

The study investigator shall complete an Unanticipated Adverse Device Effect Form and submit to the HepQuant LLC and to the reviewing Institutional Review Board (IRB) as soon as possible, but in no event later than 10 working days after the investigator first learns of the effect. HepQuant LLC is responsible for conducting an evaluation of an unanticipated adverse device effect and shall report the results of such evaluation to the Food and Drug Administration (FDA) and to all reviewing IRBs and participating investigators within 10 working days after the sponsor first receives notice of the effect. Thereafter, HepQuant LLC shall submit such additional reports concerning the effect as FDA requests.

8.4.7 REPORTING EVENTS TO PARTICIPANTS

AEs and SAEs related to the HepQuant SHUNT Liver Diagnostic Kit that are associated with device malfunction or test administration will be reported to PIs, IRBs, and through them to study participants.

Amended ICF. Unexpected AEs or SAEs may require amendment to the Informed Consent Form (ICF). Any amendments to the ICF will be distributed to all clinical site for review and approval by the appropriate regulatory bodies, ie, IRB, etc.

Study-related results will not be distributed to participants.

Incidental findings of potential clinical relevance to the participant will be conveyed to the PI and study coordinator with documentation that the findings were discussed with the participant and a follow-up plan was established.

8.4.8 EVENTS OF SPECIAL INTEREST

Any medical device incident, including defects in the HepQuant SHUNT Liver Diagnostic Kit and malfunctions with the device are considered reportable events. The clinical testing site will inform HepQuant of any of these events or situations by contacting:

Ring Central [name].

8.4.9 REPORTING OF PREGNANCY

Given that HepQuant will exclude any patient with a positive pregnancy test at screening, it is unlikely that there will be any pregnancies occurring within the relatively short time period of the participant's involvement with the study. Nonetheless, should the patient test positive for pregnancy during the study, HepQuant will report the pregnancy to study leadership, IRB, and regulatory agencies. In addition, HepQuant will request to follow pregnant women to pregnancy outcome. HepQuant expects the clinical testing site to forward appropriate source and EDC documentation.

8.4.10 PREGNANCY AND CHOLATE

Because cholates are naturally occurring with a pool size in humans of 1 to 5 g, the 20 and 40 mg doses of labeled cholates used in the HQ tests are unlikely to be harmful to a fetus. Cholate in doses of 15 mg kg⁻¹ d⁻¹ are used for treatment of liver disease in neonates and children (87,88). The 13C- and d4-cholates used in this study have been used in pregnancy to study bile acid and biliary lipid composition in women during different phases of the ovulatory cycle and in pregnancy (97-100).

However, without formal safety studies, the effects of these compounds on the fetus are not definitely known. Therefore, to be enrolled, women of child-bearing potential must have a negative pregnancy test to be enrolled in the study. Study participants will be asked to comply with pregnancy precautions, and use of approved contraceptive methods.

8.5 Unanticipated Problems

8.5.1 DEFINITION OF UNANTICIPATED PROBLEMS (UP)

Device: HepQuant SHUNT Liver Diagnostic Kit.

HepQuant LLC will use the Office for Human Research Protections (OHRP) definition of unanticipated problems involving risks to participants or others to include, in general, any incident, experience, or outcome that meets all the following criteria:

- Unexpected in terms of nature, severity, or frequency given (a) the research procedures that are described in the protocol-related documents, such as the Institutional Review Board (IRB)-approved research protocol and informed consent document; and (b) the characteristics of the participant population being studied;
- Related or possibly related to participation in the research ("possibly related" means there is a reasonable possibility that the incident, experience, or outcome may have been caused by the procedures involved in the research); and

• Suggests that the research places participants or others at a greater risk of harm (including physical, psychological, economic, or social harm) than was previously known or recognized.

This definition could include an unanticipated adverse device effect, any serious adverse effect on health or safety or any life-threatening problem or death caused by, or associated with, a device, if that effect, problem, or death was not previously identified in nature, severity, or degree of incidence in the investigational plan or application (including a supplementary plan or application), or any other unanticipated serious problem associated with a device that relates to the rights, safety, or welfare of subjects (21 CFR 812.3(s)).

8.5.2 UNANTICIPATED PROBLEM REPORTING

An investigator shall submit to HepQuant LLC and to the reviewing Institutional Review Board (IRB) a report of any unanticipated adverse device effect with the HepQuant SHUNT Liver Diagnostic Kit as soon as possible, but in no event later than 10 working days after the investigator first learns of the effect (21 CFR 812.150(a)(1)). HepQuant LLC, who will conduct an evaluation of an unanticipated adverse device effect under 812.46(b) shall report the results of such evaluation to the Food and Drug Administration (FDA) and to all reviewing IRB's and participating investigators within 10 working days after HepQuant LLC first receives notice of the effect. Thereafter HepQuant LLC shall submit such additional reports concerning the effect as FDA requests (21 CFR 812.150(b)(1)).

8.5.3 REPORTING UNANTICIPATED PROBLEMS TO PARTICIPANTS

Unanticipated problems with the HepQuant SHUNT Liver Diagnostic Kit that are associated with device malfunction, SUSARs, or other unexpected events that could potentially place participants at safety risk will be reported to Pls, IRBs, and through them to study participants.

9 STATISTICAL CONSIDERATIONS

The accuracy of the diagnostic test is commonly measured by its sensitivity and specificity or a measure that combines these quantities, such as the negative likelihood ratio: NLR = [(1-sensitivity)/specificity]. One of the primary performance goals in this trial is formulated using NLR as a primary statistical endpoint. The pre-test odds of large esophageal varices is given by $[\pi/(1-\pi)]$, where π is prevalence of large varices. The post-test odds that there are no large esophageal varices is given by: NLR x $[\pi/(1-\pi)]$. The definitions of the various measures of diagnostic accuracy and their variance are given in the equations in **Table 9**.

An approximate critical value (cv) for NLR can be calculated using equation E such that with N=400 participants the upper limit of the 95% confidence interval will rule out NLR > 0.52 if the observed NLR is smaller than the critical value. Graphically, we display the approximate critical value (cv) for NLR as a line on the ROC plot of sensitivity versus (1-specificity) as shown in **figure 10** below , which illustrates the acceptable limits for validation of the DSI cutoff. The other performance objective is that the observed sensitivity be greater than or equal to 0.85, which is shown as the lower limit of for sensitivity and serves to ensure an acceptable lower limit for the False Negative Rate (FNR). **Table 11** shows how this critical value defines the acceptable limits for sensitivity and specificity.

The evaluable sample size is N=400⁶. The total sample size of N=420 is the evaluable sample size plus an additional 20 subjects to adjust for a 5% dropout rate. For all the efficacy endpoints the **time period** between the HepQuant SHUNT test and the performance of EGD is from 0 to 42 days.

Equation label	Statistic	
A	Prior odds of large varices	$Odds = \frac{\pi}{1 - \pi}$
В	Negative likelihood ratio	$NLR = \frac{1 - sens}{spec}$
С	Positive likelihood ratio	$PLR = \frac{sens}{1 - spec}$
D	False negative rate = (1-NPV)	$FNR = 1 - \left[1 + NLR\left(\frac{\pi}{1-\pi}\right)\right]^{-1}$
E	Variance of natural logarithm of estimated NLR	$V_{nlr} = \left[\frac{sens}{(1-sens)V}\right] + \left[\frac{1-spec}{spec(N-V)}\right]$
F	Variance of natural logarithm of estimate PLR	$V_{plr} = \left[\frac{1-sens}{(sens)V}\right] + \left[\frac{spec}{(1-spec)(N-V)}\right]$
G	Miss Rate	Miss Rate = 1 - sens

Table 9: Definitions	for measures of	diagnostic accuracy
	ior measures or	anabilostic accaracy

Symbols: π = prevalence of large varices; sens = sensitivity, spec = specificity, N = trial sample size, V = number of subjects with large varices (V = N π).

9.1 Statistical Hypotheses

9.1.1 PRIMARY EFFICACY ENDPOINT (DSI ≤18.3 "RULES OUT" LARGE ESOPHAGEAL VARICES).

For each subject, the primary endpoint is the presence of large varices based on EGD examination. The primary estimands are NLR and sensitivity which then define the standard for diagnostic accuracy of DSi as a rule-out test for large varices. A primary objective is to determine whether the NLR for DSI \leq 18.3 is an improvement over the average value for NLR from 10 published studies of 2977 cases of the use of LSM plus platelet count in likelihood of large esophageal varices. Improvement will be decided if the confidence interval for the observed NLR rules out NLR > 0.52, which corresponds to the observed NLR being smaller than the approximate critical value of cv= 0.27. With this partition of the ROC outcome space, the study will conclude that the diagnostic accuracy of DSI < 18.3 is acceptable if the observed NLR is smaller than that observed in most previously published studies (**Figure 10**). The null hypothesis of NLR = 0.52 is chosen to demonstrate improvement over the diagnostic accuracy of tests evaluated in the 10 published studies of 2977 cases.

⁶ A single interim analysis is planned after the trial data set has compete DSI and EGD measurements on a minimum of 250 participants as described in Section 9.5.1.

9.1.2 SECONDARY EFFICACY ENDPOINT

Secondary efficacy endpoint (Relationship between DSI score and risk of large esophageal varices): Logistic regression will define the relationship of the probability of large esophageal varices to DSI score over the entire range of DSI. The DSI coefficient in the logistic regression model is hypothesized to be significantly larger than 0, which would confirm that the odds of large varices increases with DSI. The probability of large esophageal varices will also be measured across categories of DSI, i.e., quartiles, deciles, or other. The observed probability will be compared to the expected probability from the logistic regression analysis.

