¹ NOTE: There is some disagreement in the literature regarding the calculation of the False Negative Rate (FNR) for a test. FNR has been defined by the U.S. Food and Drug Administration in a disease-centric manner as 1 - Sensitivity ((Σ False negative) / (Σ Condition positive)), while being defined in much of the clinical literature in a test-centric manner as 1- NPV ((Σ False negative) / (Σ Predicted condition negative)). To compare to published results from the literature, in this protocol, the test-centric definition for FNR (1-NPV) has been used, and the term "miss rate" has been used to express 1-Sensitivity.

population is 20%. Each subject will have been selected to undergo a future EGD for variceal screening or surveillance according to standard criteria used in current clinical practice.

Enrolled subjects will undergo standard clinical assessment, laboratory tests, and the HepQuant SHUNT Test. The previously scheduled EGD will be performed no more than 6 weeks following the HepQuant SHUNT Test.

The relationship of DSI to large varices will be analyzed by AUROC and the diagnostic performance of the DSI cutoff \leq 18.3 will be defined by sensitivity, specificity, PPV, NPV, NLR, PLR, FNR and miss rate². The validated DSI cutoff will aid the clinician in the decision to proceed with or avoid the EGD.

Objectives:

The **primary objective** of this study is to validate DSI ≤18.3 for identifying subjects with CLD selected for future EGD for variceal screening or surveillance who are not likely to have large esophageal varices if the EGD were to be performed ("Rule Out").

The Secondary objective is to define the relationship of DSI to probability for large varices over the full range of DSI.

Exploratory objective 1 is to examine the diagnostic performance of DSI for large varices over the full range of DSI. We will generate and evaluate the AUROC (c-statistic) for DSI in likelihood of large esophageal varices. The AUROC for DSI in likelihood of large varices will be compared to the c-statistic 0.76 reported by Abrades, et al, for LSM plus platelet count (8).

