4.2.2 DETERMINING THE DSI CUTOFF 18.3 FROM THE HALT-C TRAINING DATASET

4.2.2.1 LIKELIHOOD OF LARGE ESOPHAGEAL VARICES (HALT-C TRAINING DATASET)

Uni-variable Logistic Regression. Of the 217 patients who had HepQuant SHUNT testing and protocol endoscopy, 22 had large esophageal varices. Univariate logistic regression analysis was performed using DSI as the independent variable and large varices as the outcome (**Table 3**). The relationship was highly statistically significant (p < 0.0001).

Analysis of Maximum Likelihood Estimates					
Parameter	DF	Estimate	Standard Error	Wald Chi-Square	Pr > ChiSq
Intercept	1	-6.4682	1.0014	41.7186	<.0001
DSI ruln round	1	0.1947	0.0403	23.3607	<.0001

[figure not shown]
 Table 3: Univariate Analysis of DSI for Large Esophageal Varices

Multi-variable Logistic Regression. As presented above, the gold standard for assessing risk for varices by AASLD and EASL guidelines is a diagnosis of cirrhosis. In BAVENO VI, platelet count is another major modifier of risk for clinically significant portal hypertension and risk for varices. For these reasons, we evaluated the independence of DSI as a predictor after adjusting for diagnosis of cirrhosis or stage of fibrosis and platelet count (**Table 4**).

Table 4: Multi-Variable Analysis of DSI for Large Esophageal Varices

Analysis of Maximum Likelihood Estimates					
Parameter	DF	Estimate	Standard Error	Wald Chi-Square	Pr > ChiSq
Intercept	1	-3.8601	1.5311	6.3560	0.0117
DSI_ruIn_round	1	0.1375	0.0454	9.1718	0.0025
PLT	1	-0.0117	0.00605	3.7174	0.0538
cirrho_yn	1	0.3511	0.6240	0.3166	0.5737

In these analyses, both a diagnosis of cirrhosis and platelet count were no longer statistically significant. The results demonstrate that DSI was an independent predictor of large varices and a better predictor than cirrhosis and platelet count.

Area Under the Receiver Operator Curve (AUROC). The diagnostic performance of DSI for predicting large varices was evaluated by Area under the Receiver Operating Curve (AUROC) (**Figure 3**). The c-statistic for the AUROC was 0.82. This compares favorably with an Area Under the Curve (AUC) of 0.67 (range of 0.59 to 0.72 by boot-strapping) for transient elastography that was found in the European study of Abraldes (8).

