Selecting Subjects Scheduled for EGD. The target population for application of the HepQuant SHUNT Test is the clinical population with CLD encompassed by our inclusion and exclusion criteria who are selected for EGD for variceal screening.

Categories of Etiology of CLD. We will compare the baseline characteristics of the study population across 5 general etiologic categories: viral, NAFLD/NASH, EtOH, cholestatic disease (PBC, PSC), and other miscellaneous etiologies.

Severity of CLD. The baseline characteristics of three broad categories will be compared: non-cirrhotic F3 fibrosis with platelet count <175,000 μ L⁻¹, compensated cirrhosis (Child-Pugh class A), and mildly to moderately decompensated cirrhosis (Child-Pugh class B).

HepQuant SHUNT Test. The study design is relatively straightforward and simple – one HepQuant SHUNT test is linked to the findings of one EGD performed within 6 weeks of the SHUNT Test. The primary independent variable is DSI from the HepQuant SHUNT Test. The primary dependent variable or endpoint is large esophageal varices on EGD.

The analysis of the CLD Validation Dataset will be similar to the analysis described above for the HALT-C Training Dataset. The minimal model for the HepQuant SHUNT Test will be used and the laboratory analyses have been described elsewhere in this application (see Section 6).

Large and Small Esophageal Varices (EGD finding). The primary endpoint is endoscopically-defined large esophageal varices. The presence of varices is defined as visible venous channels protruding into the esophageal lumen during air insufflation of the esophagus. Large varices are defined as medium, large, Grade 2 or 3, or variceal diameter of 5 mm or more. Varices not meeting criteria for large varices will be classified as small varices.

Any Varices (EGD finding). The endoscopic findings of patients will be defined as either large varices, small varices, or no varices. For the analysis of patients with any varices, patients with large varices will be combined with patients with small varices.

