4.3.2 LIKELIHOOD OF LARGE ESOPHAGEAL VARICES (CLD VALIDATION DATASET)

The analytical and statistical methods described in this section apply to the **primary and secondary objectives**. The steps in this analysis are similar to those used for analysis of the HALT-C Training Dataset:

- 1. Uni-variable Logistic Regression. Univariate logistic regression analysis will be performed using DSI as the independent variable and large varices as the outcome. (see **Table 3** for example of the output from this analysis).
- 2. Multi-variable Logistic Regression. As presented above, the gold standard for varices risk by AASLD guidelines is a liver biopsy diagnosis of cirrhosis. In BAVENO VI, platelet count was another major modifier of risk for clinically significant portal hypertension and risk for varices. Risk for large varices also correlates with CP class. For these reasons, we will evaluate the independence of DSI as a predictor after taking these variables into account. (see Table 4 for example of the output from this analysis).
- Receiver Operator Curve (ROC) analysis. The diagnostic performance of DSI for predicting large varices will be evaluated by Area under the Receiver Operating Curve (AUROC) and c-statistic. The optimum performance characteristics will be defined by Youden Index and sensitivity, specificity, PPV, NPV, NLR,

FNR, miss rate⁵ and 95% CIs will be defined over the spectrum of the findings (see **Figure 3** for an example of output from this analysis).

4. **Probability and Calibration Curves.** The plot of predicted probability of large varices versus DSI will be analyzed by linear regression and correlation coefficients and displayed along with 95% confidence intervals (see **Figure 4** and **5** and **Table 5** for example of the output from this analysis).

The diagnostic performance (sensitivity, specificity, PPV, NPV, NLR, FNR, miss rate⁵) of DSI cutoff 18.3 will be evaluated for large esophageal varices. In addition, we will define the relationship of DSI to the probability of large esophageal varices over the full range of DSI.

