9.4.3 STATISTICAL TESTS AND STEPS

The initial **statistical tests and steps** in the analysis of the **CLD Validation dataset** are:

Uni-variable Logistic Regression. The relationship of DSI (independent variable) to large esophageal varices (dependent variable) will first be evaluated by univariate logistic regression.

Multi-variable Logistic Regression. Independence of DSI as a predictor of large esophageal varices will be evaluated in multi-variable logistic regression analyses including other risk factors for varices. The current clinical gold standard for likelihood of varices and recommendation for EGD is a diagnosis of cirrhosis - by either liver biopsy or other criteria. Likelihood of large varices is further increased by increase in CP class. In BAVENO VI, platelet count was a major modifier of risk. For these reasons, we will evaluate the independence of DSI as a predictor of large esophageal varices adjusting for demographic variables, diagnosis of cirrhosis, stage of cirrhosis, and platelet count.

Area Under the Receiver Operator Curve (AUROC). The diagnostic performance of DSI for predicting large esophageal varices will be evaluated by Area under the Receiver Operating Curve (AUROC). The c-statistic for DSI in likelihood of large esophageal varices will be defined. The performance characteristics (sensitivity, specificity, PPV, NPV, NLR, PLR, FNR, miss rate⁷ and their 95% Cls) will be defined for DSI cutoff 18.3.

⁷ In this protocol, FNR is defined as 1-NPV and miss rate is defined as 1-Sensitivity. See the footnote in Section 1.1 for a discussion of these two measures.

Secondary efficacy endpoint (probability and calibration curves). We will evaluate the relationship of predicted probability of large varices versus DSI using logistic regression analysis and affiliated statistical tests of the significance of the association between the continuous DSI score and risk of large varices. These analytical results will be further evaluated using a calibration table to compare the observed probabilities of large varices in quartiles, deciles, or other categories of DSI to the expected probabilities from the logistic regression equation.

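### The secondary-endpoint calibration is in-sample only: it can reveal a wrong curve shape but not a shift in risk level or slope from HALT-C, and regressing predicted probability on DSI is circular

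*Combined protocol and SAP*

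**What the plan says.** The Synopsis (1.1) gives the aim: "The Secondary objective is to define the relationship of DSI to probability for large varices over the full range of DSI". Section 3 words it for DSI above 18.3. Section 9.1.2 gives the method: "Logistic regression will define the relationship of the probability of large esophageal varices to DSI score over the entire range of DSI". It then hypothesises a DSI coefficient above 0 and adds: "The observed probability will be compared to the expected probability from the logistic regression analysis". Section 9.4.3 says the calibration table will "compare the observed probabilities of large varices in quartiles, deciles, or other categories of DSI to the expected probabilities from the logistic regression equation".

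The model is fitted in the validation subjects. Item 1 of 4.3.2, under the CLD Validation Dataset heading, reads: "Univariate logistic regression analysis will be performed using DSI as the independent variable and large varices as the outcome". Section 4.3.1 adds: "The analysis of the CLD Validation Dataset will be similar to the analysis described above for the HALT-C Training Dataset". The HALT-C calibration (Tables 5 and 8) was itself done in the data used for fitting.

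Item 4 of 4.3.2 says: "The plot of predicted probability of large varices versus DSI will be analyzed by linear regression and correlation coefficients". Item 4 of 4.3.3 repeats this for varices of any size.

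No section applies the Table 3 coefficients to the new subjects. No calibration statistic or acceptance criterion is stated.

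**The concern.** The intended use is to give the clinician a likelihood of large varices, and Section 3 expects a high predicted probability to add urgency to EGD. The level of predicted risk therefore matters, as well as the direction of the association.

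The only existing risk equation comes from HALT-C, which Table 1 shows as entirely viral in etiology and entirely Child-Pugh A. This trial expects 15% viral etiology (Section 5), admits Child-Pugh B, and expects 20% prevalence against about 10%. New data are the natural place to ask whether that equation carries over. A model refitted to the new data and then compared with those same data cannot answer the question. Close agreement in such a table could easily be read as external confirmation.

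The linear regression of predicted probability on DSI carries a similar risk. It will give a high correlation that looks like evidence of fit and is not.

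**Working it through.** **Inputs.** Table 3: intercept -6.4682, slope 0.1947. Table 6: intercept -3.4685, slope 0.1405. Section 4.2.2.1: "Of the 217 patients who had HepQuant SHUNT testing and protocol endoscopy, 22 had large esophageal varices". Tables 5 and 8: group sizes, mean predicted risks and observed events. Sections 4.1.1 and 9.2.1: 20% prevalence, 400 evaluable subjects. The documents give no DSI distribution.

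**1. Reproduce the plan's figures.** DSI at 50% risk = -intercept/slope.
- Large varices: 6.4682/0.1947 = 33.22 (stated 33.2).
- Any size: 3.4685/0.1405 = 24.69 (stated 24.7).

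**2. The identity.** A maximum-likelihood logistic model with an intercept solves Σ(y - p) = 0 and ΣDSI(y - p) = 0. The first equation makes total expected equal total observed. Refitting the outcome on the model's own logit returns intercept 0 and slope 1. The HALT-C tables show the first identity:
- Table 5 expected: 0.490×16 + 0.240×8 + 0.143×39 + 0.044×154 = 22.1, against 22 observed.
- Table 8 expected: 0.732×19 + 0.537×15 + 0.450×29 + 0.347×44 + 0.248×64 + 0.161×46 = 73.6, against 74 observed.

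The differences are rounding.

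**3. What the category table can and cannot detect.** Simulation, N = 400, 1,000 runs per scenario. Assumptions: lognormal DSI with median 18.35 and log-SD 0.288, chosen to approximate HALT-C, and a quartile chi-square on 2 df. The plan names no test.

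| True relation | Refit O/E and slope | Quartile test rejects | R² of predicted risk on DSI (median) |
|---|---|---|---|
| HALT-C equation correct | 1.000, 1.000 | 4.9% | 0.81 |
| Same slope, prevalence 20% | 1.000, 1.000 | 6.0% | 0.93 |
| Half slope, prevalence 20% | 1.000, 1.000 | 5.6% | 0.97 |
| DSI unrelated, prevalence 20% | 1.000, 1.000 | 6.5% | 0.998 |
| Step at 18.3 (3% below, 37% above) | 1.000, 1.000 | 99.9% | 0.95 |
| Non-monotone | 1.000, 1.000 | 99.2% | 0.98 |

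The table detects a wrong shape. For a change of level or slope it rejects at about the nominal 5%. R² is highest when DSI carries no information, so the item 4 regression says nothing about fit.

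**4. Possible size of a shift.** Mean predicted risk over HALT-C's own DSI values must equal 22/217 = 10.1%.
- If prevalence is 20% and DSI is distributed as in HALT-C: O/E = 0.20/0.101 = 1.97, about 2.
- If the rise comes entirely from higher DSI: O/E is about 1. With lognormal DSI (median 18.35, log-SD 0.27 to 0.33), an upward shift of roughly 5 to 6 points makes the HALT-C equation predict 20%. A 3-point shift gives O/E of 1.26 to 1.46.

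**5. Is the external check informative at this size?** In the simulation, if the HALT-C equation is correct, O/E at N = 400 averages 1.00 (95% range 0.75 to 1.30). With the same DSI distribution and 20% prevalence it averages 2.13 (1.76 to 2.53). The latter is above 1.97 because the assumed distribution gives a mean risk of 9.3%, slightly under HALT-C's 10.1%.

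**The case against.** A reader might infer that a locked HALT-C equation was due for validation and was dropped. The documents do not support that. Section 4.3.2 cites Table 3 only as an example of output. What is carried forward for validation is the cutoff 18.3, plus an exploratory STAT cutoff. The secondary objective is to define a relationship, and fitting a model in the intended population is a legitimate way to do so.

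A reader might also infer that the calibration check cannot fail. It is planned by DSI category, and step 3 shows that it can fail for a wrong shape. The test of the DSI coefficient can fail as well.

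A third inference is that the HALT-C equation will under-predict two-fold. That holds DSI fixed while doubling prevalence, and the documents point the other way. Section 5.2 says DSI rises with fibrosis stage and Child-Pugh class, and this trial adds Child-Pugh B and requires low platelets in F3. HALT-C restricted to F4 plus low-platelet F3 already gives (17 + 4)/(93 + 25) = 17.8% (Section 4.3.1), so much of the rise may be case mix.

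Transport is also partly addressed elsewhere. The cutoff is tested on new data through NLR and sensitivity, performance is reported by etiology (9.6.1.1), and regressions are run within etiologies of over 50 subjects (9.6.1.2).

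All of this stands and limits the point. It leaves three facts untouched: the calibration is apparent only, no analysis tests the HALT-C risk equation on new subjects, and item 4 is circular.

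**Conclusion.** The point holds as a missing external check, not a broken commitment. On the natural reading of 4.3.2, 9.1.2 and 9.4.3, observed risk is compared with a model fitted to the same subjects. That comparison can show a misshapen curve but not a departure from HALT-C in level or slope. This follows from the likelihood equations and needs no assumption. The same is true of the circularity in item 4 of 4.3.2 and 4.3.3.

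The possible size does rest on an assumption. At 20% prevalence, O/E for the HALT-C equation would lie between about 1 and about 2, depending on how far DSI itself is higher in this trial. The planned analysis cannot say where in that range the trial falls.

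Optimism in the refitted model should be small, with one predictor and about 0.20 × 400 = 80 events, so the gap is transport rather than overfitting. The test of the DSI coefficient and the primary endpoint are unaffected.

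**What to change.** - **9.1.2 and 9.4.3:** apply the fixed Table 3 equation, logit(p) = -6.4682 + 0.1947 × DSI, to the validation subjects. Report the observed/expected ratio, calibration intercept and calibration slope with 95% CIs, and the table by DSI quartile, the grouping that the Synopsis and Section 3 already name. Then present the refitted model as the update, with its calibration labelled apparent. Bootstrap correction is optional.
- **4.3.2 and 4.3.3, item 4:** delete the linear regression and correlation of predicted probability on DSI.

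The cost is a few lines of analysis code and a short text change; no new data are needed. The downside for the sponsor is that the check may show miscalibration.
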